Cardiovascular diseases (CVDs) remain a significant concern for global health, representing a considerable burden in terms of morbidity and mortality. The prevalence of CVDs is continuously increasing, and their impact on physical health and quality of life (QoL) is profound (Saglietto et al., 2021; Townsend et al., 2022). Risk factors such as obesity, hypertension, hypercholesterolemia, aging, and insufficient physical activity contribute to CVDs (Kraus et al., 2019; Tian & Meng, 2019). Physical activity (PA) has emerged as a crucial therapeutic strategy in the management and prevention of CVDs, helping to improve cardiovascular function, fitness, and overall QoL (Franklin et al., 2022). Physical training, especially aerobic training (AT) and resistance training (RT), has drawn attention as a non-pharmacological approach to managing CVDs. RT has shown potential benefits in improving muscle function, skeletal muscle mass, insulin sensitivity, blood pressure regulation, and endothelial function (Oliveira et al., 2018; Trevizani et al., 2018). Recently, isometric exercises, once considered to be contraindicated for treating cardiovascular diseases, have been shown to be the most effective in managing conditions like hypertension (Edwards et al., 2024). The complexity of CVDs requires a holistic approach to exercise prescription. Multicomponent training (MCT) protocols aim to address various aspects of fitness, targeting not only cardiovascular endurance but also muscle strength, mobility, and balance (Bouaziz et al., 2016). These components can collectively contribute to improved functional capacity and enhanced QoL (Bouaziz et al., 2016). The impact of integrating multiple exercise modalities into an MCT for CVDs remains underexplored. It is not yet entirely clear which protocol may be the most efficient for improving physiological and psychological parameters in individuals with a history of cardiovascular problems that are currently stable.

AIMS AND HYPOTHESES OF THE PROJECT

Primary outcome:

The purpose of this study is to evaluate the effectiveness of MCT on physiological parameters, physical fitness, mental well-being, and quality of life in individuals with a history of cardiovascular problems that are currently stable, compared to an integrated multicomponent training protocol with isometric exercises (IMCT) and a waitlist control group (WLCG).

Secondary outcome:

Assess the enjoyment/motivation in performing the different training protocols, as well as adherence through analysis of dropout rates and the number of completed sessions.

Hypothesis:

We hypothesize that both groups will report improvements in physiological parameters, physical fitness, mental well-being, and overall quality of life compared to the WLCG. Additionally, the IMCT group will show superior improvements in physiological parameters compared to the MCT group.

CHARACTERISTICS OF PARTICIPANTS

The study aims to recruit at least 30 individuals with a history of cardiovascular problems, currently stable, aged between 45–80 years.

Inclusion Criteria

- Women/Men
- 45–80 years old
- Absence of severe medical conditions (unstable coronary artery disease, decompensated heart failure, severe pulmonary hypertension) or acute conditions that would prevent safe participation in physical activity according to the guidelines of the American College of Sports Medicine (ACSM), American Heart Association (AHA), and the European Society of Cardiology (ESC) (Billinger et al., 2014; Gary Liguori & ACSM, 2021; Pelliccia et al., 2021; Williams et al., 2007)
- History of cardiovascular dysfunctions currently stabilized
- Sedentary lifestyle (individuals not having followed WHO guidelines for aerobic and resistance exercise in the last 3 months)

Exclusion Criteria

- Smokers
- Expected absence for more than one week during the intervention period
- Absence of a medical certificate of suitability for non-competitive sports
- Severe musculoskeletal or joint disorders with significant mobility limitations

- Presence of joint pain, dizziness, chest pain, or angina during physical activity
- High blood pressure: PBP \geq 160/100 (untreated))

SAMPLE SIZE

A priori power analysis (Kang, 2021) with a Type I error of 0.05 and Type II error rate of 0.05 (95% statistical power) calculated that 10 participants per group would be sufficient to observe moderate interaction effects between “Time x Group.”

RECRUITMENT METHOD

Participants will be recruited through the "Amici di Cuore" association located at [name], and will be randomly assigned to one of three groups:

- MCT
- IMCT
- WLCG

data collection

Before the intervention, all participants, with prior approval from their primary care physician, will sign an informed consent form. All participants will undergo physiological evaluations and functional tests before (T0) and at the end of the intervention (T1). Data will be collected anonymously, assigning each participant a random identification number.

Measurements:

Anthropometric Parameters:

- Height
- Weight
- BMI

Hemodynamic Parameters:

- Resting Heart rate (RHR)
- Peripheral Systolic Blood Pressure (P-SBP)
- Peripheral Dyastolic Blood Pressure (P-DBP)

Physical Parameters:

- Timed Up and GO (TUG)
- 30 Seconds Chair Stand Test (30”CST)
- 2 Minutes Step Test (TMST)
- Handgrip Strength Test (HGS)

Psychological Parameters:

- SF-36
- BREQ-3

Experimental Design

After initial evaluations, participants will be randomly assigned to one of the three groups. All protocols will last 24 weeks and take place at the Angiulli Artistic Gymnastics Society (Bari).

Sessions will be conducted in small groups. These groups will be closely supervised by exercise professionals, specialists in adapted physical activity (AFA), to ensure participant safety, maintain proper intensity, and correct execution technique. To monitor and regulate training intensity (internal load) during sessions, the Borg Perceived Exertion Scale (RPE) (6-20) will be used at the end of each exercise set to regulate the load to Borg = 13-15 points (Gary Liguori & ACSM, 2021). Participants will be familiarized with the scale beforehand.

Participants in the WLCG will not perform any structured physical activity during the entire intervention period, maintaining their usual lifestyle and placed on a waiting list to receive adapted physical activity after the 24-week intervention period.

Multi-component Training:

Each training session will include an initial muscle activation phase lasting 10 minutes (low-intensity walking, Borg = 10-11) to increase heart rate, improve muscle blood flow, and prepare the main joints for the subsequent work phase. This will be followed by a main 40-minute exercise period (aerobic exercise, mobility exercises, and resistance training) and a 10-minute cool-down period (breathing exercises and stretching).

The cardiorespiratory training will consist of progressive aerobic exercises: controlled and rhythmic jumping jacks, step-ups on a stable platform (such as a low step or a stable surface), alternating knee lifts, rapid lateral steps, or lateral leg raises. Finally, 3 minutes of low-intensity walking will facilitate recovery for the next training phase.

The mobility training will consist of specific exercises (thoracic extensions, cat-cow, overhead stretching with a stick, and active internal hip rotations) targeting the main joints. These will be performed to the maximum (1 to 3 sets) but avoiding pain. The duration will gradually increase from 30 to 60 seconds per repetition, repeating from one to three times. Rest intervals of 30 to 60 seconds will be provided between sets and exercises.

The resistance training will consist of exercises targeting different muscle groups (8 exercises): quadriceps (leg extension with ankle weights/half squat with a chair), biceps (unilateral dumbbell curl), shoulders (dumbbell shoulder press), triceps (dumbbell French press), chest (dumbbell chest press/dumbbell flyes), and back (dumbbell rows). The resistance training program will follow the principle of gradual progressive load. Initially, participants will perform one set of 10-15 repetitions, which will increase to three sets of 10-15 repetitions during the intervention. Load adjustments will be made to ensure that the perceived effort (RPE) remains between 13 and 15 on the Borg Scale (6-20). During the protocol, participants will be given rest intervals of 60 to 120 seconds between sets and exercises. To prevent early muscle fatigue, exercises will be performed using an alternating training method based on muscle group division (upper body exercises will be performed in the first session and lower body exercises in the second).

The cool-down period will consist of breathing exercises and stretching. Stretching will be performed by seeking the maximum stretch on all the main muscle groups (1 to 3 sets per muscle group) while avoiding joint pain. The duration will gradually increase from 10 to 30 seconds per stretch, repeating from one to three times for a total of 60 seconds per exercise.

Isometric Multi-component Training:

Each training session will include an initial phase of muscle activation lasting 10 minutes (low-intensity walking, Borg = 10-11) to increase heart rate, improve blood flow to muscles, and prepare the main joints for the subsequent work phase. This will be followed by a main 40-minute exercise period (aerobic exercise, mobility exercises, and isometric training) and a 10-minute cool-down period (breathing exercises and stretching). The cardiorespiratory training will consist of progressive aerobic exercises: controlled and rhythmic jumping jacks, step-ups on a stable platform (such as a low step or a stable surface), alternating knee lifts, quick lateral steps, or lateral leg raises. Finally, 3 minutes of low-intensity walking will facilitate recovery for the subsequent phase of training.

The mobility training will consist of specific exercises (thoracic extensions, cat-to-cow movements, overhead stretching with a stick, and active internal hip rotation) targeting the main joints, performed to the maximum (from 1 to 3 sets), while avoiding pain. The duration will gradually increase from 30 to 60 seconds per repetition, repeating from one to three times. Recovery intervals of 30 to 60 seconds will be allowed between sets and exercises.

The isometric training will focus on exercises targeting different muscle groups (8 exercises): quadriceps (isometric leg extension/wall squat), biceps brachii (isometric dumbbell curl), shoulders (isometric lateral raises with dumbbells), triceps brachii (isometric French press with dumbbells), pectoralis major (isometric dumbbell chest press/dumbbell flyes), latissimus dorsi (isometric dumbbell rows). The isometric training program will follow the principle of gradual progressive loading. Initially, participants will perform one set of 30 seconds, which will increase to three sets of 30 seconds over the course of the intervention. Load adjustments will be made to ensure that the perceived effort (RPE) stays between 13 and 15 on the Borg Scale (6-20). During the protocol, participants will be given recovery intervals of 60 to 120 seconds between sets and exercises. To prevent early muscle fatigue, exercises will be performed using an alternating training method based on splitting muscle groups (upper body exercises will be performed in the first session and lower body exercises in the second).

The cool-down period will consist of breathing exercises and stretching. Stretching will be performed seeking maximum elongation of all major muscle groups (from 1 to 3 sets per muscle group), avoiding joint pain. The duration will gradually increase from 10 to 30 seconds per stretch, repeating from one to three times for a total of 60 seconds per exercise.

EXPECTED RESULTS AND RELEVANCE

Although the positive effect of physical activity in individuals with a history of cardiovascular problems, even in stable conditions, has already been demonstrated, the impact of integrating multiple exercise modalities in a MCT or IMCT in the field of cardiovascular diseases (CVDs) remains underexplored. It is still not entirely clear what the most efficient protocol might be for improving physiological and psychological parameters in individuals with a history of cardiovascular issues, currently stabilized. At the end of this exercise program, we expect to observe a general improvement in physiological, motor, and psychological parameters, with a greater increase in the IMCT group, particularly in relation to physiological parameters. Furthermore, we believe that this new research modality could offer a novel approach to proposing a physical activity that is particularly engaging, motivating, and designed to improve the quality of life (both physiologically and psychologically).

To date, physical exercise remains a crucial factor for promoting psychological and biological improvements with profound implications for public health. Indeed, physical activity promises to be an important tool to be used alone or in combination with traditional therapies (such as drugs or medications), to enhance the effectiveness of prevention and treatment strategies for various chronic non-communicable diseases.

Critical Situations and Potential Negative Effects

The main risks, though rare, but considered, may include:

- Acute cardiovascular events: participants with a history of pre-existing cardiovascular conditions, currently stabilized, may, in rare cases, experience episodes of angina, arrhythmias, or increased blood pressure during the training sessions.
- Falls or injuries: the exercises proposed, if performed incorrectly or without supervision, could pose a risk of falls or musculoskeletal injuries.

Risk Management Strategies

- Continuous monitoring during sessions: each training group will be supervised by professionals specialized in adapted physical activity (APA). The Borg scale will be used to monitor the perceived effort during the exercise, keeping it within a moderate range (13-15 points).
- Emergency procedures: to ensure safety, an emergency plan will be in place. APA operators are adequately trained to recognize any symptoms of fatigue or cardiovascular discomfort and to intervene promptly if necessary.
- Medical support: before starting, participants will provide an exercise clearance evaluation signed by the attending doctor/cardiologist, ensuring they are fit to participate. Additionally, the proximity (about 3 minutes by car, 1.4 km) to the main local medical facility (Policlinico di Bari – University Hospital Consortium, [name]) has been

considered to allow for quick access to emergency services.

Documentation in the Research Protocol

All preventive measures and management strategies are included in the protocol:

- In the "intervention" section, the structure of the training sessions, the control of exercise intensity, and supervision by qualified personnel are provided.
- The management of cardiovascular and musculoskeletal risks is addressed in the inclusion/exclusion criteria, which exclude participants with acute or unstable conditions to ensure the safety of the study sample.

REFERENCES

Aguiar, L. T., Nadeau, S., Britto, R. R., Teixeira-Salmela, L. F., Martins, J. C., Samora, G. A. R., Da Silva Júnior, J. A., & Faria, C. D. C. D. M. (2020). Effects of aerobic training on physical activity in people with stroke: A randomized controlled trial. *NeuroRehabilitation*, 46(3), 391–401. <https://doi.org/10.3233/NRE-193013>

Billinger, S. A., Arena, R., Bernhardt, J., Eng, J. J., Franklin, B. A., Johnson, C. M., MacKay-Lyons, M., Macko, R. F., Mead, G. E., Roth, E. J., Shaughnessy, M., & Tang, A. (2014). Physical Activity and Exercise Recommendations for Stroke Survivors: A Statement for Healthcare Professionals From the American Heart Association/American Stroke Association. *Stroke*, 45(8), 2532–2553. <https://doi.org/10.1161/STR.0000000000000022>

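### Adjusting the 24-week value for its pre-randomisation baseline would usually be somewhat more precise than the conventional Time x Group comparison, and the plan names no model or covariate

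*Combined protocol and SAP*

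**What the plan says.** The combined protocol and SAP has no statistical analysis section. Its one reference to a between-group outcome analysis is under Sample Size, where the power analysis "calculated that 10 participants per group would be sufficient to observe moderate interaction effects between “Time x Group". Both error rates are set at 5% there, so the power claimed is 95%. No numeric effect size, correlation between time points, SD, test family, model, covariate or contrast is given.

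The timing of the measurements is clear. Under data collection: "All participants will undergo physiological evaluations and functional tests before (T0) and at the end of the intervention (T1"). Under Experimental Design: "After initial evaluations, participants will be randomly assigned to one of the three groups". Each outcome therefore has one baseline value, taken before allocation, and one value at 24 weeks.

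The hypotheses are comparisons between arms. Both exercise arms are expected to improve relative to the waitlist (WLCG), and "the IMCT group will show superior improvements in physiological parameters compared to the MCT group". Expected Results and Relevance repeats that direction ("with a greater increase in the IMCT group, particularly in relation to physiological parameters"). Neither place gives a size.

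**The concern.** With two time points and complete data, the conventional Time x Group test in a repeated-measures ANOVA is the same as a one-way ANOVA on the change T1 − T0. That analysis fixes the coefficient on T0 at 1. Unless the true slope of T1 on T0 is also 1, part of any chance baseline difference between arms stays in the estimated effect and adds to its variance. A model of T1 on arm and T0 estimates the slope instead. Because T0 precedes randomisation, that model is also valid and targets the same between-arm difference.

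What is at stake is precision. With 10 per arm and three comparisons of interest, one of them between two active programmes, intervals may be wider than the data already being collected allow.

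**Working it through.** **Inputs from the documents.** Alpha 0.05; power 95%; 3 arms of 10 (N = 30); 2 time points; T0 before randomisation.

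**Assumed, because the documents do not give them.** The correlation rho between T0 and T1; the SD ratio k = SD(T1)/SD(T0); Cohen's f for a moderate effect; and the noncentrality convention in step 1.

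**Step 1. The plan's own figure.** For the within-between interaction with two times, take lambda = f² × N × 2/(1 − rho), with 2 and 27 degrees of freedom. The stated 10 per group can be neither confirmed nor refuted without f and rho. With f = 0.25, power at N = 30 is 63.5% at rho = 0.5 and reaches 95% at rho = 0.783, where lambda = 0.0625 × 60/0.217 = 17.3. At rho = 0.5, 95% power needs f of about 0.38.

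**Step 2. Variance of a between-arm difference, adjusted relative to change score.** Set SD(T0) = 1.

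- Change score, per participant: 1 + k² − 2·rho·k = k²(1 − rho²) + (1 − rho·k)².
- Adjusted, per participant: k²(1 − rho²), multiplied by 1 + 1/(30 − 3 − 2) = 1.04 for estimating the slope.

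The extra term (1 − rho·k)² is the average effect of chance T0 imbalance, carried into the change-score estimate with factor −(1 − rho·k). Better precision and protection against imbalance are therefore one benefit and should not be counted twice. At k = 1 and rho = 0.5 the split is 1.00 = 0.75 + 0.25.

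With k = 1 the ratio reduces to 1.04 × (1 + rho)/2:

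| rho | Ratio | Variance with adjustment |
|---|---|---|
| 0.5 | 0.780 | 22% lower |
| 0.7 | 0.884 | 12% lower |
| 0.783 | 0.927 | 7% lower |
| 0.8 | 0.936 | 6% lower |
| 0.9 | 0.988 | 1% lower |
| 0.95 | 1.014 | 1.4% higher |

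Break-even is at rho = 2/1.04 − 1 = 0.923. Simulated trials of 3 × 10 (200,000 per setting) gave 0.780, 0.883 and 0.935 at rho 0.5, 0.7 and 0.8.

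**Step 3. The gain where the plan's power claim would hold.** At f = 0.25 and rho = 0.783, adjustment moves power from 95.0% to 96.3% (lambda/0.927, with 2 and 26 degrees of freedom). The 95% CI half-width for one pairwise difference goes from t(27) × √(4 × 0.217/10) = 0.60 SD to t(26) × √(2 × (1 − 0.783²) × 1.04/10) = 0.58 SD. If f were 0.30 or 0.35, the matching rho is 0.69 or 0.58 and the variance gain 12% or 18%.

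**Step 4. Unequal SDs.** Ratios at rho 0.5, 0.7 and 0.8 are 0.594, 0.653 and 0.666 for k = 0.8, and 0.906, 1.005 and 1.037 for k = 1.2. At k = 1.2 adjustment is slightly worse for rho between about 0.69 and 0.91.

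**Step 5. How much can be lost.** With a slope common to all arms, k²(1 − rho²) can never exceed the change-score variance, so the ratio is at most 1.04 at N = 30. With 8 per arm at T1 (assumed dropout) the limit is 1 + 1/(24 − 3 − 2) = 1.053.

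The limit does not carry over to unequal slopes. Two assumed examples, each simulated 200,000 times with SD(T0) = 1 and one pooled slope fitted:

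- Slopes 0.95 (MCT), 0.6 (IMCT), 0.95 (WLCG), residual variance 0.2: MCT vs WLCG variance is 10% higher than with the change score; the two IMCT comparisons are 13% lower.
- Slopes 1 (MCT), 1 (IMCT), 0.7 (WLCG), residual variance 0.36: IMCT vs MCT is 7% higher; the other two are 1% lower.

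**The case against.** The strongest reply is that this criticises an analysis the plan has not chosen. The interaction is mentioned once, in a power statement, and a longitudinal Time x Group model with a common baseline mean would itself satisfy that wording. This stands: the documents neither require nor exclude baseline adjustment, so the loss is conditional on the conventional form being used. For the same reason the point is subordinate to the wider absence of an analysis model.

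It is also fair to say that no magnitude comes from the documents and that no single figure describes a list of outcomes as varied as blood pressure, functional tests and questionnaires. The SD ratio alone moves the result at rho = 0.8 from 33% lower to 4% higher.

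A reader might infer more than the material supports, in four ways:

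- **That the change-score comparison is biased or inflates Type I error.** It does neither over randomisation; both estimators target the same difference.
- **That 22% is the expected gain.** That needs rho = 0.5, where 10 per arm reaches 95% power only if f is about 0.38. At the conventional f = 0.25 the figure consistent with the plan's claim is about 7%.
- **That adjustment can never cost more than 4%.** That limit needs a common slope and all 30 participants measured at T1. Slopes that differ between trained and untrained arms cannot be excluded.
- **That 10 per arm is shown to be wrong.** Nothing here shows that.

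**Conclusion.** The point holds as a cheap improvement, not as an error in the plan. The only analysis named is, in its conventional form, valid but usually less precise than adjusting T1 for T0. The best single figure is about 7% lower variance for each between-arm difference. It rests on equal SDs, a common slope, 30 participants with complete data, f = 0.25 and the noncentrality convention in step 1. Across rho from 0.5 to 0.9 with equal SDs the range is 22% to 1% lower. The possible loss is small under a common slope, and larger for a single comparison if slopes differ. No hypothesis becomes untestable without the change, and the practical gain may be slight.

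**What to change.** For each continuous outcome measured at T0 and T1, prespecify a linear model of T1 on randomised arm with that outcome's T0 value as covariate. Alternatively, prespecify a constrained longitudinal Time x Group model with a common T0 mean across arms; this keeps the target named under Sample Size and can include randomised participants who lack T1. Report the three adjusted differences (MCT vs WLCG, IMCT vs WLCG, IMCT vs MCT) with 95% CIs. Fixing the choice beforehand also prevents choosing between two defensible analyses once any baseline imbalance has been seen.

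The change is wording only and needs no new data. Its statistical cost is one residual degree of freedom (27 to 26), about 4% variance inflation for estimating the slope (5.3% with 8 per arm), already counted in the net ratios above, and a linear common-slope assumption that is hard to check with 10 per arm. If the missing analysis model is raised as a separate point, this belongs there as one line of that fix.

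### The 95% power is stated only for the non-directional Time x Group interaction and does not carry over to IMCT versus MCT; adjust T1 for T0 and rest that claim on its own pairwise contrast

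*Combined protocol and SAP*

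**What the plan says.** The Sample Size section reports a power analysis "with a Type I error of 0.05 and Type II error rate of 0.05 (95% statistical power") and concludes that "10 participants per group would be sufficient to observe moderate interaction effects between" Time and Group. Alpha and power appear nowhere else. The section gives no number for moderate, no T0–T1 correlation and no outcome.

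The Hypothesis section is worded in pairwise comparisons. It first expects both trained arms to improve relative to waitlist: "We hypothesize that both groups will report improvements in physiological parameters, physical fitness, mental well-being, and overall quality of life compared to the WLCG". It then adds that "the IMCT group will show superior improvements in physiological parameters compared to the MCT group". Expected Results and Relevance repeats the second prediction: "with a greater increase in the IMCT group, particularly in relation to physiological parameters".

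On timing, the data collection section states: "All participants will undergo physiological evaluations and functional tests before (T0) and at the end of the intervention (T1"). Experimental Design states: "After initial evaluations, participants will be randomly assigned to one of the three groups". The baseline value therefore precedes randomisation. Measurements lists several candidate physiological variables, including resting heart rate and systolic and diastolic pressure.

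There is no analysis section. No model is named, and follow-up contrasts are neither planned nor excluded.

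**The concern.** A three-group, two-time interaction asks whether the three mean changes are all equal. It does not say which arms differ or in which direction, and it can be significant when IMCT and MCT are identical and both exceed waitlist. The one power figure in the documents therefore does not tell a reader how well the trial can address IMCT over MCT.

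Precision is the second issue. Under standard repeated-measures ANOVA with two times, the interaction test is the same as comparing change scores. That is valid, but it gives wider intervals than adjusting T1 for the T0 value already collected.

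At stake is whether the IMCT versus MCT result is reported with its own estimate and interval, and whether readers wrongly credit that comparison with 95% power.

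**Working it through.** **Inputs.** From the documents: alpha 0.05, power 0.95, three arms of 10 (N = 30), two measurements. Not given, so assumed: effect size f, correlation rho, two-sided contrasts. All figures assume complete data and independent participants.

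**1. The plan's own figure.** For the interaction, lambda = f² × N × 2/(1 − rho), tested as F on 2 and 27 df. Power of 95% needs lambda = 17.32.

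| f (assumed) | rho (assumed) | lambda | Power at N = 30 |
|---|---|---|---|
| 0.25 | 0.3 | 0.0625 × 60/0.7 = 5.36 | 49% |
| 0.25 | 0.5 | 7.50 | 64% |
| 0.25 | 0.7 | 12.50 | 86% |
| 0.25 | 0.78 | 17.05 | 95% |
| 0.40 | 0.5 | 0.16 × 60/0.5 = 19.20 | 97% |

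The 95% is attainable under some inputs and not under others.

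**2. Trained arms equal.** In units of the SD of change, let both trained arms exceed waitlist by g. Then lambda = 10 × (2/3) × g². Setting this to 17.32 gives g = √(17.32 × 3/20) = 1.61. The interaction then has 95% power. The IMCT versus MCT difference is zero, so that contrast rejects at its 5% error rate.

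**3. Trained arms unequal, taking the 95% at face value.** Let IMCT gain G over waitlist and MCT gain qG. Then lambda = 10 × G² × 2(1 − q + q²)/3 = 17.32, and the contrast has noncentrality G(1 − q) × √(10/2) on 27 df. At q = 1/2, G = 1.86, the difference is 0.93, the noncentrality is 2.08 and power is 52%.

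| MCT share q of IMCT's gain | 0 | 1/4 | 1/3 | 1/2 | 2/3 | 3/4 | 1 |
|---|---|---|---|---|---|---|---|
| Power, IMCT vs MCT (change scores) | 93% | 82% | 75% | 52% | 26% | 16% | 5% |

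The documents do not give q.

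**4. Precision that does not depend on the 95%.** The half-width of the 95% interval for IMCT versus MCT is t(0.975, 27) × √(2/10) = 2.052 × 0.447 = 0.92 SD of change. Power of 80% needs 2.906 × 0.447 = 1.30 SD of change. Multiplying by √(2(1 − rho)) converts this to 1.54, 1.30, 1.01 and 0.82 baseline SD at rho 0.3, 0.5, 0.7 and 0.8.

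**5. Gain from adjusting for T0.** In large samples the ratio of interval widths, adjusted to change score, is √((1 + rho)/2). This gives 0.81, 0.87, 0.92 and 0.95 at rho 0.3, 0.5, 0.7 and 0.8. Simulation at 10 per arm, which includes the lost degree of freedom and chance baseline imbalance, gives 0.823, 0.884, 0.941 and 0.969. Intervals are therefore narrower by about 18%, 12%, 6% and 3%.

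**6. Error control.** For one outcome with no true differences, three ungated contrasts gave a familywise error of 11.8% in simulation. Testing them only after a significant 2-df group test gave 5.0%. This gate costs the IMCT versus MCT contrast at most about 2 points of power if the 95% holds. At assumed f = 0.25 with no MCT effect, power under baseline adjustment falls from 65% to 58% (rho 0.3), 73% to 67% (rho 0.5) and 88% to 85% (rho 0.7). Separately, three independent physiological measures each tested at 0.05 would give 1 − 0.95³ = 14% familywise error.

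**The case against.** The strongest reply is that the interaction appears only as the basis for the sample size, and that the gap is an absent analysis section rather than a wrong choice. Much of that stands. A reader might infer four stronger things, and the documents support none of them.

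- *That a significant interaction will be reported as IMCT superiority.* No section says so.
- *That the 95% power is wrong.* With f, rho and outcome unstated it cannot be refuted, and f = 0.40 at rho 0.5 more than meets it.
- *That the interaction or change scores are invalid.* They are not. Baseline adjustment is a precision gain, not the correction of an error. Its larger gains are at low rho, where holding 95% power at N = 30 would need f of 0.45 (rho 0.3) or 0.38 (rho 0.5). At f = 0.25 the 95% is reached only near rho 0.78, where intervals narrow by about 4%.
- *That IMCT versus MCT must be called exploratory.* Low power does not make a prespecified, error-controlled contrast exploratory. On the 95% anchor its power is 75% to 93% when MCT achieves one third or less of IMCT's gain, and the recruitment target is a minimum of 30.

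Nor do the documents rank IMCT over MCT above the waitlist comparisons; the Hypothesis section adds it after them. What the reply does not remove is that the only stated power belongs to a test that cannot by itself identify an IMCT–MCT difference, while the documents twice predict one.

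**Conclusion.** The concern holds in limited form. The 95% power refers to the interaction and says nothing definite about IMCT versus MCT. If the 95% is accepted, power for that contrast runs from about 93% down to the 5% error rate, depending on a share that the documents do not give. The ±0.92 and 1.30 SD of change figures need only the stated 10 per arm, a two-sided 5% level and the usual normal model. The gains from adjustment depend on the assumed rho. Dropout would widen the intervals, and so would positive correlation between participants who train in the same small group. Neither is allowed for here.

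**What to change.** 1. For outcomes measured at T0 and T1, analyse T1 by assigned arm, adjusted for the T0 value.
2. Prespecify the pairwise contrasts. Base any IMCT-over-MCT statement on that contrast and its 95% interval, for one lead physiological measure named before data are seen, or under a stated rule across measures such as Holm.
3. State how familywise error is held across the contrasts. Testing them only after a significant 2-df group test is one valid way with three arms and one outcome, at the power cost shown above.
4. In the sample-size text, report the f, rho and outcome used, and say that the 95% refers to the interaction and not to IMCT versus MCT. State the limited precision of that contrast at 10 per arm; an exploratory label is optional.

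The cost is a paragraph of text and one degree of freedom. No new data are needed, because T0 is already collected before randomisation.
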